9.4. Statistical Analyses

Note: As Amendment 2 will serve to discontinue the study to further enrollment, limited safety and efficacy analyses will be performed. Listings will be substituted for summary tables for efficacy analyses. Summary tables will only be provided for selected safety analyses.

9.4.1. Efficacy Analyses

The ORR will be summarized in accordance with both RECIST v1.1 [REDACTED]. It is defined as the percentage of subjects having CR or PR per RECIST v1.1; [REDACTED]. The ORR as determined by the investigator and their 95% exact binomial CIs will be summarized.

Progression-free survival will be summarized per RECIST v1.1 [REDACTED]. It is defined as the time from the start of combination therapy until the earliest date at which progression criteria are met (as determined by investigator evaluation of objective radiographic disease assessment per RECIST v1.1 [REDACTED]) or death due to any cause, if occurring sooner than disease progression. Censoring of PFS will follow FDA guidance (FDA 2007). Details will be provided in the Statistical Analysis Plan. Total number of subjects who progressed or died and number of subjects censored will be summarized. Kaplan-Meier estimate of PFS will be provided with 95% CIs.

Duration of response will be summarized per RECIST v1.1 [REDACTED]. It is defined as the time from the earliest date of CR/PR per RECIST v1.1, [REDACTED], until the earliest date at which progression criteria are met (as determined by investigator evaluation of radiographic disease assessment per RECIST v1.1 [REDACTED] or death due to any cause, if occurring sooner than disease progression. Censoring of DOR will follow the same algorithm as the censoring of PFS noted above. Total number of objective responders, number of subjects who progressed or died, and number of subjects censored will be summarized. Kaplan-Meier estimates of DOR will be provided with 95% CIs.

9.4.2. Safety Analyses

The clinical safety data (vital signs, physical examinations, ECGs, laboratory tests, and AEs) will be summarized using descriptive statistics (eg, mean, frequency) using the safety population. Summary tables may be replaced with listings when appropriate. For example, an AE frequency table may be replaced with a listing if it only contains a few unique preferred terms reported on relatively few subjects.

9.4.2.1. Adverse Events

A TEAE is any AE either reported for the first time or worsening of a pre-existing event after first dose of study treatment. Analysis of AEs will be limited to TEAEs, but data listings will include all AEs regardless of their timing to study drug administration. Adverse events will be tabulated by the MedDRA preferred term and system organ class. Severity of AEs will be based on the NCI CTCAE v4.03 using Grades 1 through 5.

The subset of AEs considered by the investigator to have a relationship to study drug will be considered to be treatment-related AEs. If the investigator does not specify the relationship of

the AE to study drug, the AE will be considered treatment-related. The incidence of AEs and treatment-related AEs will be tabulated.

9.4.2.2. Clinical Laboratory Tests

Laboratory data will be classified into Grades 1 through 4 using CTCAE v4.03. The following summaries will be produced for the laboratory data:

- Number and percentage of subjects with worst postbaseline CTCAE grade (regardless of baseline value). Each subject will be counted only for the worst grade observed postbaseline.
- Shift tables from baseline to the worst postbaseline value using CTCAE grade.
- For laboratory parameters where CTCAE grades are not defined, shift tables to the worst postbaseline value using the low/normal/high classifications based on laboratory reference ranges.

9.4.2.3. Vital Signs

Descriptive statistics and mean change from baseline will be determined for vital signs (blood pressure, pulse, respiratory rate, and body temperature) at each assessment time. Vital sign results will be reviewed for clinically notable abnormalities (see [Table 31](#)), and subjects exhibiting clinically notable vital sign abnormalities will be listed. A value will be considered an "alert" value if it is outside the established range and shows a > 25% change from baseline.

Table 31: Criteria for Clinically Notable Vital Sign Abnormalities

Parameter	High Threshold	Low Threshold
Systolic blood pressure	> 155 mmHg	< 85 mmHg
Diastolic blood pressure	> 100 mmHg	< 40 mmHg
Pulse	> 100 bpm	< 45 bpm
Temperature	> 38°C	< 35.5°C
Respiratory rate	> 24/min	< 8/min

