
 • Any liver function abnormalities that meet the definition of Hy's law^a • Any grade encephalopathy. • ≥ Grade 2 ocular irAEs. • Grade 4 irAEs will be considered a DLT regardless of duration. • Any ≥ Grade 3 nonhematologic toxicity EXCEPT: 
 – Transient (≤ 72 hours) abnormal laboratory values without associated clinically significant signs or symptoms. – Nausea, vomiting, and diarrhea adequately controlled with medical therapy within 48 hours. – Grade 3 rash in the absence of desquamation, with no mucosal involvement, that does not require systemic steroids and that resolves to Grade 1 in ≤ 14 days. – ≥ Grade 3 changes in amylase and lipase that is not associated with symptoms or clinical manifestations of pancreatitis. – Asymptomatic changes in lipid profiles. – Singular or nonfasting elevations in blood glucose (ie, blood glucose excursions will be considered toxicities if fasting blood glucose is elevated on 2 separate occasions). – Grade 3 irAE that improves to ≤ Grade 1 in ≤ 14 days by appropriate care or with corticosteroid therapy. – Grade 3 IRR that returns to Grade 1 in less than 6 hours
Hematologic

 • ≥ Grade 3 thrombocytopenia with clinically significant bleeding (requires hospitalization, transfusion of blood products, or other urgent medical intervention). • Grade 4 neutropenia or thrombocytopenia lasting > 7 days. • ≥ Grade 3 febrile neutropenia (ANC < 1.0 × 10⁹/L and fever > 101°F/38.3°C). • Grade 4 (life-threatening) anemia not explained by underlying disease.
General

 • Subjects being unable to receive ≥ 75% of study drug doses during the DLT observation period because of toxicity, even if the toxicity does not meet DLT criteria defined above. Note: Exceptions include the DLT exclusions mentioned above. • Any death not clearly due to the underlying disease or extraneous causes.

Note: Transient (≤ 72 hours) abnormal laboratory values without associated clinically significant signs or symptoms based on investigator determination will not be considered a DLT.

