Moderate	Increased tachycardia Fever (up to 41°C) Diarrhea with hyperactive bowel sounds Diaphoresis with normal skin color	Hyperreflexia Inducible clonus Ocular clonus (slow continuous lateral eye movements) Myoclonus	Easily startled Increased confusion Agitation and hypervigilance	Rhabdomyolysis Metabolic acidosis Renal failure Disseminated intravascular coagulopathy (secondary to hyperthermia)
Severe	Temperature often more than 41°C (Secondary to increased tone)	Increased muscle tone (lower limb > upper) Spontaneous clonus Substantial myoclonus or hyperreflexia	Delirium Coma	As above

Source: [Boyer and Shannon 2005](#).

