7.5.3. Vital Signs and Weight

Vital sign measurements include blood pressure, pulse, respiratory rate, body temperature, and weight. Clinically notable abnormalities that are considered clinically significant in the judgment of the investigator are to be reported as AEs.

7.5.4. 12-Lead Electrocardiograms

Baseline 12-lead ECGs will be obtained at screening, with additional ECGs obtained at EOT, and as clinically indicated for all subjects. Additional triplicate ECGs will also be obtained at Cycle 1 Day 1 predose and 2 hours after the first dose of epacadostat, and at Cycle 2 Day 1 predose and 2 hours after administration of epacadostat (see Table 26).

Clinically significant abnormal findings at screening will be recorded as medical history. Clinically significant abnormal findings after the first dose of study treatment should be recorded as an AE. All 12-lead ECGs will be performed with the subject in a recumbent or semirecumbent position after 5 minutes of rest.

The 12-lead ECG readings will be interpreted by the investigator at the site to be used for immediate subject management. The decision to include or exclude a subject or to withdraw a subject from the study treatment based on an ECG flagged as "Abnormal, Clinically Significant" is the responsibility of the investigator, in consultation with the medical monitor, as appropriate. Clinically notable abnormalities that are considered clinically significant in the judgment of the investigator are to be reported as AEs. In the event that a single QTc is > 480 msec at screening, the subject may enroll if the average QTc for 3 consecutive ECGs is < 480 msec or with approval from the medical monitor. Prolonged QTc intervals must be read by a cardiologist. For subjects with an intraventricular conduction delay (QRS interval > 120 msec) at screening, the JTc interval may be used in place of the QTc with medical monitor approval. In addition, the JTc interval should be used for all subsequent assessments.

Table 26: Schedule of ECG Assessments

Timepoint	Screening	Cycle 1 Day 1	Cycle 2 Day 1	EOT
Predose	X	X – triplicate	X - triplicate	X
2 hours (± 5 min) after epacadostat dose	N/A	X – triplicate	X - triplicate	N/A

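### Does the 25% change condition leave the vital-sign alert label unable to flag an abnormal body temperature, and does that call for a change?

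*Combined protocol and SAP*

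**What the plan says.** Section 9.4.2.3 asks for descriptive statistics and mean change from baseline for "vital signs (blood pressure, pulse, respiratory rate, and body temperature) at each assessment time". It then does two separate things.

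- **Listing.** Results are compared with Table 31, and "subjects exhibiting clinically notable vital sign abnormalities will be listed". Table 31 gives a high and a low limit for systolic pressure, diastolic pressure, pulse, temperature and respiratory rate. For temperature these are > 38°C and < 35.5°C. There is no percent condition in the table or in this sentence.
- **Alert label.** A value counts as an alert if it is "outside the established range and shows a > 25% change from baseline". The same rule covers all parameters, with no separate rule for temperature.

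Section 7.5.3 gives a further route that does not use the alert rule: "Clinically notable abnormalities that are considered clinically significant in the judgment of the investigator are to be reported as AEs".

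Two other places give absolute temperatures that serve as yardsticks. The dose-limiting toxicity table (Table 7, Section 5.4.2) defines febrile neutropenia partly by "fever > 101°F/38.3°C". The serotonin syndrome table (Table 17, Section 5.4.6) includes "Fever (up to 41°C") among the moderate signs, and says that temperature often exceeds 41°C in severe cases.

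**The concern.** A percent change suits a quantity that varies by a sizeable fraction of its usual value. Pulse and blood pressure do; body temperature in °C does not. The zero of the Celsius scale is arbitrary, and the whole range between the two Table 31 limits spans only 2.5 degrees. Joining a 25% change to the Table 31 limits therefore seems to switch the alert off for one of the five parameters.

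Two consequences could follow. First, a reader might take an absence of temperature alerts as reassurance, although it would be true whatever fevers occurred. Secondly, if a programmer used the alert rule to select the rows of the clinically notable listing, no realistic fever would appear in it. In a trial of three combined immune-targeting agents, whose protocol uses fever in a dose-limiting toxicity definition, that second outcome would be unwelcome.

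**Working it through.** **Inputs.** The Table 31 limits and the 25% condition come from Section 9.4.2.3. The 38.3°C figure comes from Table 7 and the 41°C figure from Table 17. The documents give no baseline temperature. I assume one within Table 31 (35.5 to 38°C), use 37.0°C as a worked value, and test 34 and 40°C. The plan states no derived figure here to reproduce.

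**Step 1: reading needed for a temperature alert.** Inside the assumed range the 25% condition is always stricter than the Table 31 limit, so the triggers are 1.25 × baseline (high) and 0.75 × baseline (low).

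| Baseline (°C) | High trigger (°C) | Low trigger (°C) |
|---|---|---|
| 35.5 | 1.25 × 35.5 = 44.375 | 0.75 × 35.5 = 26.625 |
| 37.0 | 1.25 × 37.0 = 46.25 | 0.75 × 37.0 = 27.75 |
| 38.0 | 1.25 × 38.0 = 47.5 | 0.75 × 38.0 = 28.5 |

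**Step 2: size of the changes the protocol itself describes.**

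- 37 to 38°C: 38/37 − 1 = +2.7%
- 37 to 38.3°C: 38.3/37 − 1 = +3.5%
- 37 to 41°C: 41/37 − 1 = +10.8%
- 37 to 35.5°C: 35.5/37 − 1 = −4.1%
- 35.5 to 41°C: 41/35.5 − 1 = +15.5%
- 35.5 to 38°C, from one Table 31 limit to the other: 38/35.5 − 1 = +7.0%

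None comes near 25%.

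**Step 3: sensitivity.** A baseline of 34°C gives a high trigger of 1.25 × 34 = 42.5°C. A baseline of 40°C gives a low trigger of 0.75 × 40 = 30.0°C. Percent change also depends on the unit. In Fahrenheit, 35.5°C is 95.9°F, and 1.25 × 95.9 = 119.875°F = 48.8°C. On the low side, 38°C is 100.4°F, and 0.75 × 100.4 = 75.3°F = 24.1°C. Neither variation makes the label usable.

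**Step 4: is this peculiar to temperature?** The baseline at which a Table 31 limit is exactly a 25% change is limit/1.25 for the high side and limit/0.75 for the low side.

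| Parameter | Table 31 range | High limit ÷ 1.25 | Low limit ÷ 0.75 |
|---|---|---|---|
| Systolic (mmHg) | 85 to 155 | 124 | 113.3 |
| Diastolic (mmHg) | 40 to 100 | 80 | 53.3 |
| Pulse (bpm) | 45 to 100 | 80 | 60 |
| Respiratory rate (/min) | 8 to 24 | 19.2 | 10.7 |
| Temperature (°C) | 35.5 to 38 | 30.4 | 47.3 |

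A value that crosses the high limit meets the 25% condition if baseline is below the third column. One that crosses the low limit meets it if baseline is above the fourth. For the first four parameters both cut-offs lie inside the Table 31 range, so the rule works. For temperature both lie outside it.

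**Step 5: what depends on the label.** The alert value appears in one sentence of Section 9.4.2.3 and nowhere else in the text available.

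- The listing in the same section is tied to the term *clinically notable*, which is also the term in Table 31's title. The alert is a different term, introduced afterwards.
- Section 9.4.2.4 has the same structure for ECGs and lists on thresholds alone.
- The Phase 2 enrolment pause (Section 4.1.2) depends on Grade 3 or higher immune-related events.
- Safety Monitoring Committee analyses are left to its charter (Section 9.5).

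A subject who reaches 38.5°C is therefore listed. If the investigator judges the value clinically significant, it also enters the adverse event data, which are graded and tabulated under Section 9.4.2.1.

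**The case for a change.** The strongest case for a change is that a label which cannot realistically apply to one of its five parameters should not stand when a sentence or two would correct it. The rule was evidently written with blood pressure, pulse and respiratory rate in mind and carried over to temperature. Section 9.4.2.3 also does not say in so many words that the alert is a second label and not a filter on the listing, and a hurried programmer could combine the two.

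The arithmetic part of this stands in full. The filter part is hypothetical, because it requires a departure from the text: the listing sentence carries no percent condition, and neither does the table it uses.

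The possible revisions also bring little.

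- Defining a temperature alert by the Table 31 range alone makes it identical to the clinically notable criterion, which already produces a listing.
- Defining it by an absolute change in °C needs a figure the documents do not contain, and it would serve a label that nothing uses.
- Stating that the listing relies on Table 31 repeats what the section already says.

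The practical reach is small as well. Under Amendment 2 enrolment is closed, Treatment Group B enrolled nobody (Section 4.1), and safety summary tables are limited to selected analyses (Section 9.4).

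**Conclusion.** The observation is true, but the plan can stand. For baselines of 35.5 to 38°C, a temperature alert would need a reading above 44.4 to 47.5°C or below 26.6 to 28.5°C, so the label is in practice confined to blood pressure, pulse and respiratory rate. That range of baselines is an assumption, but baselines of 34 and 40°C lead to the same conclusion.

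No estimate, table, listing or decision in the documents depends on the label. Abnormal temperatures reach the reader through the Table 31 listing, the descriptive summaries and adverse event reporting. This rests on reading the listing sentence as written, with Table 31 as its only criterion. On that reading, an analyst needs only to know that an absence of temperature alerts carries no information about fever. This is a loosely drawn label definition that sensible programming absorbs, and amending it would not improve the safety analysis.

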9.4.2.4. Electrocardiograms

Descriptive statistics and mean change from baseline will be determined for each ECG parameter at each assessment time. Electrocardiogram results will be reviewed for clinically notable abnormalities according to predefined criteria ([Table 32](#)). Subjects exhibiting clinically notable ECG abnormalities will be listed.

Table 32: Criteria for Clinically Notable Electrocardiogram Abnormalities

Parameter	High Threshold	Low Threshold
QTcF	> 480 ms	< 295 ms
PR	> 220 ms	< 75 ms
QRS	> 120 ms	< 50 ms
QT	> 500 ms	< 300 ms

QTcF = Fridericia correction.

9.4.2.5. Adverse Events of Special Interest

Adverse events of special interest include irAEs that are seen with immunotherapy and any other observed autoimmune phenomenon.

An overall summary of irAEs will include number (%) of subjects reporting any irAEs, any Grade 3 or 4 irAEs, any treatment-related irAEs, any fatal irAEs, and any irAEs leading to treatment interruption/dose reduction/discontinuation.

[REDACTED]

9.5. Analyses for the Safety Monitoring Committee

An SMC will review safety data at regular intervals throughout Phase 2 of the study. The frequency of meetings will be contingent upon enrollment and availability of safety data for analysis and review. Details regarding the analyses needed for the committee will be specified in the SMC charter.

9.6. Interim Analysis

No interim analysis is planned.

10. ETHICAL CONSIDERATIONS AND ADMINISTRATIVE PROCEDURES

10.1. Investigator Responsibilities

This study will be performed in accordance with ethical principles that originate in the Declaration of Helsinki and conducted in adherence to the study Protocol; GCPs as defined in Title 21 of the US CFR Parts 11, 50, 54, 56, and 312; ICH E6 GCP consolidated guidelines; and local regulatory requirements as applicable to the study locations.

The investigator will be responsible for:

- Permitting study-related monitoring, sponsor audits, IRB/IEC review, and regulatory inspections by providing direct access to source data and other relevant clinical study documents.
 - Monitoring: Qualified representatives of the sponsor or its designee, study monitors, will monitor the study according to a predetermined plan. The investigator must allow the study monitors to review any study materials and subject records at each monitoring visit.
 - Auditing: Qualified representatives of the sponsor or its designee may audit the clinical study site and study data to evaluate compliance with the Protocol, applicable local clinical study regulations, and overall study conduct. The investigator must allow the auditors to review original source records and study documentation for all subjects.
 - Regulatory inspection: Regulatory authorities may conduct an inspection of the study and the site at any time during the development of an investigational product. The investigator and staff are expected to cooperate with the inspectors and allow access to all source documents supporting the eCRFs and other study-related documents. The investigator must immediately notify the sponsor when contacted by any regulatory authority for the purposes of conducting an inspection.
- Obtaining informed consent and ensuring that the study subjects' questions have been answered and the subjects fully understand study procedures:
 - Informed consent must be obtained before any study-related procedures are conducted, unless otherwise specified by the Protocol.
 - Informed consent must be obtained using the IRB/IEC-approved version in a language that is native and understandable to the subject. A template will be provided by the sponsor or its designee. The sponsor or its designee must review and acknowledge the site-specific changes to the ICF template. The ICF must include a statement that the sponsor or its designee and regulatory authorities have direct access to subject records.

- Obtaining approval from the IRB/IEC before the start of the study and for any changes to the clinical study Protocol, important Protocol deviations, routine updates, and safety information in accordance with institutional requirements and local law.
 - The investigator is responsible for ensuring that the safety reports provided by the sponsor are reviewed and processed in accordance with regulatory requirements and with the policies and procedures established by the IRB/IEC.
- Adhering to the Protocol as described in this document and agreeing that changes to the Protocol procedures, with the exception of medical emergencies, must be discussed and approved, first, by the sponsor or its designee and, second, by the IRB/IEC. Each investigator is responsible for enrolling subjects who have met the specified eligibility criteria.
- Retaining records in accordance with all local, national, and regulatory laws, but for a minimum period of at least 2 years after the last marketing application approval in an ICH region and until there are no pending or contemplated marketing applications in an ICH region, or if not approved, 2 years after the termination of the test article for investigation to ensure the availability of study documentation should it become necessary for the sponsor or a regulatory authority to review.
 - The investigator must not destroy any records associated with the study without receiving approval from the sponsor. The investigator must notify the sponsor or its designee in the event of accidental loss or destruction of any study records. If the investigator leaves the institution where the study was conducted, the sponsor or its designee must be contacted to arrange alternative record storage options.
 - All eCRF data entered by the site (including audit trail), as well as computer hardware and software (for accessing the data), will be maintained or made available at the site in compliance with applicable record retention regulations. The sponsor will retain the original eCRF data and audit trail.

10.2. Accountability, Handling, and Disposal of Study Drug

The investigator is responsible for drug accountability at the study site; however, some of the drug accountability duties may be assigned to an appropriate pharmacist or other designee. Inventory and accountability records must be maintained and readily available for inspection by the study monitor and are open to inspection at any time by any applicable regulatory authorities. The investigator or designee must maintain records that document:

- Delivery of study drug to the study site.
- Inventory of study drug at the site.
- Subject use of the study drug including pill or unit counts from each supply dispensed.
- Return of study drug to the investigator or designee by subjects.

The investigational product must be used only in accordance with the Protocol. The investigator will also maintain records adequately documenting that the subjects were provided the specified

study drug. These records should include dates, quantities, and any available batch or serial numbers or unique code numbers assigned to the investigational product and study subjects.

Completed accountability records will be archived by the site. The investigator or designee will be expected to collect and retain all used, unused, and partially used containers of study drug until verified by the study monitor (unless otherwise agreed to by the sponsor). At the conclusion of the study, the investigator or designee will oversee shipment of any remaining study drug back to the sponsor or its designee for destruction according to institutional standard operating procedures. If local procedures mandate on-site destruction of investigational supply, the site should (where local procedures allow) maintain the investigational supply until the study monitor inspects the accountability records in order to evaluate compliance and accuracy of accountability by the investigative site. At sites where the study drug is destroyed before monitor inspection, the monitors rely on documentation of destruction per the site SOP.

